In this project we will establish the relationship between the electric field generated by conventional, sponge-based tDCS and its effect on dual task performance. In doing so, we will provide first-of-its-kind insight into the degree of inter-subject variability in generated electric field in older adults, as well as the component(s) of this field that underlie observed functional benefits. We have hypothesized, based upon the evidence described above, that 1) when using conventional tDCS, the average nE over the left dlPFC ‘drives’ observed dual tasking improvements, and therefore, 2) multichannel tDCS that optimizes flow to this region will maximize benefit and reduce variance. If these hypotheses are supported, our project will establish a methodology and analytical pipeline to understand, control, and optimize tDCS dosage—a discovery with significant applications to our work and that of the entire field of noninvasive brain stimulation. If our hypotheses are not supported, our electric field mapping approach will nevertheless produce an invaluable dataset from which voxel-based and other computational and

statistical approaches may be used to test additional hypotheses to advance our understanding and optimization of tDCS.

References:

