The immediate after-effects of conventional tDCS on dual task walking performance are beneficial yet relatively variable across older adults with high baseline dual task costs to gait speed. We extracted data from all older adult participants described in the previous section who had “at-risk” baseline dual task costs to gait speed of $>20\%$ despite no overt disease or illness ($n=20$; 12 women; dual task cost $\mu\pm\sigma=26\pm13\%$; age= 75 ± 6 years). Conventional tDCS targeting the left dlPFC reduced the dual task cost to gait speed in all but one participant, and at the group level, significantly reduced this outcome as compared to sham stimulation ($p=0.002$). While the mean absolute pre-to-post change in dual task cost from pre-to-post tDCS was 12 percentage points, the standard deviation of change was 10 with a range of 35. These data demonstrate that 1) we can recruit older adults with poor dual task performance, 2) conventional tDCS holds promise to improve dual task performance in these vulnerable individuals, and 3) the effects of tDCS, while beneficial, are quite variable across individuals.

The degree to which conventional tDCS is “on-target” correlates with dual task improvements, yet varies across participants. We completed a pilot RCT in which 20 older adults with slow gait and mild-to-moderate executive dysfunction, yet who were without overt disease or illness, were randomized to a 2- week, 10-session conventional tDCS intervention targeting the left dlPFC (NCT02436915).⁵⁶ tDCS, compared to sham, reduced dual task costs to gait speed and postural sway speed, and improved cognition as assessed by the Montreal Cognitive Assessment (MoCA), at a two-week follow-up ($p<0.05$). Twelve participants also completed a baseline structural brain MRI. Six of these were then randomized to tDCS. We used Stimweaver with each MRI to model generated electric fields based upon the electrode placement and flow parameters used for the intervention. The normal component of the electric field (nE) averaged over the left dlPFC varied considerably, and, correlated closely with reduced dual task costs to gait speed at follow-up ($r^2=0.80$, $p<0.05$). In contrast, the nE over the right dlPFC did not correlate with dual task changes (not shown). These data give us confidence that the left dlPFC is an important target for dual task performance, and optimizing tDCS will likely maximize its effectiveness and reduce inter-subject variability.

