tDCS: Each participant will be exposed to a single session of conventional tDCS, optimized tDCS, and two shams, delivered using the Startim-8™ device and software (Neuroelectrics Corp, Cambridge MA). This system enables custom amounts of current to be delivered via conventional 25 cm² sponges or through an array of up to eight Pi™ (3 cm²) gel Ag/AgCl electrodes placed on the scalp according to the 10-20 EEG convention. This system also enables blinding of study personnel and participants to the type of stimulation being administered. Staff and participants will complete a blinding questionnaire after each session. Participants will complete a short side effects questionnaire at the beginning and end of every session,⁹⁰ on which they will be asked to state whether they received tDCS or sham intervention on that visit, and their confidence in this belief.

Conventional tDCS: The anode will be placed over F3 and the cathode over the contralateral supraorbital margin (Figure 5). At the beginning of stimulation, the current will be increased manually from 0.1 mA, in 0.1 mA increments over 60 seconds, up to a maximum of 1.8 mA. Participants will be instructed to notify study personnel if and when they feel any uncomfortable sensation. The ramp-up will be stopped at this point and for the remainder of the session tDCS will be delivered at an intensity of 0.1 mA below the highest level reached. At the end of each session, current will be automatically ramped down to 0.0 mA over a 60 second period. The same ramp-up/ramp-down procedures will be used across the other active conditions.

Conventional sham: A conventional sham will be used to maximize blinding of conventional sponge-based stimulation. The same sponge placement, ramp-up procedure, and session duration described above will be used; however, current will be automatically ramped down 60 seconds after ramp-up.⁹¹

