Optimized tDCS: This intervention will utilize eight gel electrodes with placement and current parameters optimized to the cohort , with the goal of generating an average nE over the dlPFC of the same size as the one delivered by a conventional montage using sponges in an average subject at 1.5 mA of current (we will use prior data from older adults to define this average target).. The direct current delivered by any one electrode will however never exceed 2.0 mA; the total amount of current from all electrodes will not exceed 4 mA. Each 20- minute session will begin and end with a 60-second ramp up/down of current amplitude to maximize comfort.

Optimized sham: An active sham will be used in which very low-level currents (0.5 mA max) are

transferred between the same electrodes used in the active condition throughout the entire 20-minute session. This intervention will be optimized to deliver currents designed to not significantly influence their cortical tissue, but still mimic the cutaneous sensations induced by tDCS. We have shown that this active sham effectively blinds participants and operators to stimulation condition and does not affect functional outcomes.⁶⁶

Pre/post tDCS assessments: Participants will complete a dual task paradigm before, immediately after, and one hour after tDCS administration. Procedures will follow published recommendations^{6,92,93} that produce excellent test-retest reliability.⁹⁴⁻⁹⁹ We have used this paradigm within our research and laboratory for over ten years. Participants will complete two, 60-second trials in each of six conditions:

- Condition 1: Single task: seated cognitive task (see below for description).
- Condition 2: Single task: standing.
- Condition 3: Single task: walking.
- Condition 4: Dual task: standing with cognitive task.
- Condition 5: Dual task: walking with cognitive task.
- Condition 6: Single task: fast walking

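### Does scaling optimized tDCS to the sponge field at 1.5 mA, when sponge current may reach 1.8 mA, undermine the comparison of the two montages?

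*Protocol*

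**What the plan says.** In the Protocol, Study Procedures, the paragraph on optimized tDCS sets the target for average nE over the dlPFC as "of the same size as the one delivered by a conventional montage using sponges in an average subject at 1.5 mA of current". Prior data from older adults are to define that value, and no number is given. The same paragraph says that each "session will begin and end with a 60-second ramp up/down of current amplitude to maximize comfort".

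The paragraph on conventional tDCS raises the sponge current "in 0.1 mA increments over 60 seconds, up to a maximum of 1.8 mA". Participants are to "notify study personnel if and when they feel any uncomfortable sensation". The ramp-up then stops, and for the rest of the session "tDCS will be delivered at an intensity of 0.1 mA below the highest level reached". It closes with: "The same ramp-up/ramp-down procedures will be used across the other active conditions".

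The Background section expects that "multichannel tDCS that optimizes flow to this region will maximize benefit and reduce variance". The section on previous studies concludes from pilot modelling that "optimizing tDCS will likely maximize its effectiveness and reduce inter-subject variability". Hypothesis 1 predicts a correlation between the effect of conventional tDCS and average left-dlPFC nE. Hypothesis 2A predicts a larger improvement with optimized tDCS than with conventional tDCS or either sham. Hypothesis 2B predicts more consistent effects than with conventional tDCS.

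The list under Data Collection Instruments has a blinding and a side-effects questionnaire for tDCS sessions. No listed form is identified as recording current. The SAP's models use stimulation condition, time, their interaction, age, sex and BMI. They use neither nE nor current.

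**The concern.** If average nE drives benefit, a montage whose average nE is pegged to 1.5 mA of sponge current seems badly placed to beat a sponge session that may run at 1.8 mA. The protocol gives no basis for the 1.5 mA reference, no expected nE for either active condition and no forecast of how many participants will stop the ramp early. The direction of the on-target difference therefore cannot be read from the documents.

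There also seem to be two ramp descriptions: one driven by tolerance for sponges, and one that is only timed for the gel array.

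Two things would be at stake. A positive, null or reversed gel-versus-sponge result could not be traced to montage or to field strength if delivered current were unknown. And if nE for Hypothesis 1 were modelled at one nominal current, differences in delivered current would become error in the predictor and weaken the correlation. Current not captured at the session might not be recoverable later.

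**Working it through.** The plan gives no nE value, power or sample-size figure on this point, so there is nothing to reproduce. The check is a ratio, a few illustrations and a comparison of texts.

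**1. Ratio of fields.** Inputs from Study Procedures: reference 1.5 mA, ceiling 1.8 mA, step-down 0.1 mA. Assumptions: field is proportional to current for a fixed montage and head, and the gel montage is delivered in full. Optimized target nE / sponge nE = 1.5 / I, where I is the delivered sponge current in the average subject.

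| Sponge session | I (mA) | 1.5 / I |
|---|---|---|
| No discomfort | 1.8 | 0.83 |
| Discomfort at 1.8 | 1.7 | 0.88 |
| Discomfort at 1.6 | 1.5 | 1.00 |
| Discomfort at 1.3 | 1.2 | 1.25 |
| Discomfort at 1.1 | 1.0 | 1.50 |

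The sign depends on how many participants stop early. A delivered mean of 1.5 mA is possible under a 1.8 mA ceiling.

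**2. Equal mean field does not rule out Hypothesis 2A.** The Background attributes variable response to diffuse current and individual anatomy, so better targeting is one route to a larger effect. Less spread in nE is another. As an illustration, assume lognormal nE and a square-root response, with s² = ln(1 + CV²). Break-even sponge current is then 1.5 × exp[(s²_conv − s²_opt)/4]. With an optimized CV of 0.2 (s² = 0.0392):
- conventional CV 0.4 (s² = 0.1484): 1.54 mA;
- conventional CV 0.6 (s² = 0.3075): 1.60 mA.

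**3. Hypothesis 1, if nE were modelled at a nominal current.** Let g be field per mA, independent of current I. The correlation is multiplied by CVg / √[CVg² + CVI²(1 + CVg²)]. The current mixes below are constructed so that the mean is 1.5 mA. CVg = 0.3 is assumed. Power is by Fisher z, two-sided 0.05, with an assumed 20 MRI participants.

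| Assumed mix | CVI | Factor | Power, true r = 0.6 | Power, r² = 0.80 |
|---|---|---|---|---|
| 75% at 1.4, 25% at 1.8 mA | 0.115 | 0.93 | 0.74 | 0.998 |
| 50% at 1.2, 50% at 1.8 mA | 0.200 | 0.82 | 0.60 | 0.97 |
| 37.5% at 1.0, 62.5% at 1.8 mA | 0.258 | 0.74 | 0.51 | 0.91 |

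Without attenuation, power at r = 0.6 is 0.82. The value r² = 0.80 is the protocol's pilot figure. It comes from six participants and is probably optimistic, but it shows that the fall to 0.51 reflects the chosen r as much as the attenuation.

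**4. Hypothesis 2B.** With CVg = 0.3 and CVI = 0.20, the CV of conventional nE is √(0.09 + 0.04 + 0.0036) = 0.37, against 0.30 at constant current. Tolerance-driven current therefore also bears on how a consistency result is explained, just as it does for Hypothesis 2A.

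**5. The texts side by side.**
- The 1.5 mA figure defines a modelling target for a cohort-level montage. The 1.8 mA figure is an individual upper limit. Both can hold at once.
- The conventional paragraph extends its ramp procedures to the other active condition. The optimized paragraph's 60-second ramp has the same length and is compatible with that. Only how a 0.1 mA step-down is spread over eight electrodes is left unsaid.
- The instrument list gives titles only and is incomplete. It omits the SPPB, Geriatric Depression Scale, Brief Pain Inventory and gradCPT, all required at the screening visit, and the adverse-event case report forms. It names no device output. Absence from it is weak evidence that current is not kept.
- The protocol's one described precedent for computing nE, the pilot, used the electrode positions and current settings of the actual intervention. The section on research importance says the fields produced by both active conditions will be modelled. No text specifies a nominal current.

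**The case for a change.** The strongest case for acting is that this is a study of tDCS dosage, so the dose delivered is not a side issue. The sponge ramp is manual and depends on the participant, no text commits to keeping the final setting, and recording it costs one field per session. Nor do the documents say that 1.5 mA is the expected mean. They quote discomfort or mild pain in 10 to 18% of tDCS recipients. If 18% ran at an assumed 1.0 mA and the rest at 1.8 mA, the mean would be 0.18 × 1.0 + 0.82 × 1.8 = 1.66 mA and the optimized-to-sponge ratio 1.5/1.66, or about 0.91.

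Part of this stands. Delivered current is worth keeping, and a sentence on the basis for 1.5 mA would help readers. But the quoted rates are not specific to this ramp, and participants may report milder sensations, so the direction stays open. Matching average field while improving focus may also be deliberate. The setting is chosen in 0.1 mA steps on a software-driven device, and anyone modelling an individual's field needs a current to enter. The harm to Hypothesis 1 requires the analysts to depart from their own pilot method. That is missing detail, not a flaw in design or analysis.

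**Conclusion.** No change to the plan is called for. The optimized target is 0.83 of sponge nE at the 1.8 mA ceiling and equal to it at 1.5 mA, given proportional fields and full delivery of the gel montage. That gap does not make the passages contradictory, and it does not bias the randomized comparisons. Gel versus sponge, and each active condition versus sham, remain valid tests of the montages as delivered. The SAP's models are untouched because they use neither current nor nE.

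What depends on delivered current is the mechanistic explanation of Hypotheses 1, 2A and 2B, and individual nE is available only for those who take the optional MRI. The attenuation factors of 0.93 to 0.74 and the power losses apply only if nE is modelled at a nominal current, and their CVs, current mixes and sample size are all assumed. Analysts following the pilot's approach would use the current actually applied, and the basis for the 1.5 mA reference can be given when the modelling is reported.

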Research Lab. Two T1 datasets will be acquired: one with fat-suppression to optimize brain and CSF segmentation and another one without it to optimize skull and skin segmentation. Field-of-view will encompass all the head with coverage up to C1/2 vertebrae. Silent brain infarcts will be identified as focal lesions appearing hyper-intense on T2 and hypo-intense on T2 FLAIR scans. White matter lesions will be identified as periventricular and subcortical regions appearing hyper-intense on T2 FLAIR. Lesion diameters and volumes will be automatically calculated using an in-house AFNI and Free Surfer combination pipeline and the Lesion Segmentation Tool for SPM with manual edits as necessary. All volumes will be normalized as a percentage of the total brain parenchyma volume.

Parameters: T1: 362 s, TR/TE=2530/3.32 ms, flip angle=7°, 1 mm³ isotropic resolution, matrix=256X256; T2: 283 s, TR/TE= 3200/284 ms, 1mm²isotropic resolution, matrix=256X256; T2 FLAIR:422 s, TR/TE=6000/388 ms, flip angle=120°, thickness=1.0 mm, 0.49x0.49 mm in-plane resolution, matrix=512X512. BOLD MRI will utilize a standard echo-planar imaging sequence with the following parameters: repetition time/echo time (TR/TE)= 1050/34.8ms; 65° flip angle; 230x230mm field of view (FOV) with a 104x104 acquisition matrix; thickness/gap (THK)=4mm/1mm with 2x2mm² in-plane resolution. Anatomical MRI will be acquired after the BOLD sequences with the T2-weighted FLAIR sequence (TR/TE/TI = 6000/279/2100ms, 1.0mm isotropic, 256x256mm, 160 slices/slab) and a 3D magnetization prepared rapid gradient echo (MP-RAGE) sequence (TR/TE/TI = 7.8/3.1/600ms; 1.0mm slice thickness, 52 slices; bandwidth = 122Hz per pixel; 10° flip angle; 240x240mm FOV with 256x192 acquisition matrix).

There will be one optional MRI visit, approximately 50 minutes in duration.

Data Management

All data collected for analysis will be de-identified and assigned a unique study number. Data collection forms will be kept in a locked file cabinet in the office of the PI at Hebrew SeniorLife. Data will be entered and stored on a password-protected secure server at Hebrew SeniorLife.

The Institute for Aging Research primarily employs the REDCap system to facilitate data management operations. REDCap is a full-featured clinical trials data management system (DMS) accessible to data entry and data analysis workstations using secure Web technologies. The REDCap product is developed and maintained by Vanderbilt University in cooperation with REDCap Consortium members, including Hebrew SeniorLife. HSL hosts and maintains a dedicated instance of REDCap for use across our research enterprise. Each research study is provided separate project workspace in which all of the study data are stored in a MySQL relational database on the private corporate network behind several firewalls and located physically within the HSL data center.

Data collected will be stripped of identifiers. Data will be assigned a code number and no personal identifying information will be associated with study data in any format, including electronically. Only the investigators will know information about a particular subject. Identifying information about a subject will be stored in locked computer files and cabinets and will not be used during the discussion, presentation, or publication of any research data.

Data will be kept on a secure, password protected Hebrew SeniorLife server in a REDCap Database. Only study members at the Hebrew SeniorLife site will have access to the REDCap database. All

hard copy forms will be kept in a locked filing cabinet that only study members will be able to access.

We will follow the current Hebrew SeniorLife Record Management, Retention, Disposition and Destruction Guidelines for this study. Identifiers will be kept for 7 years following the completion of the study. At this time destruction of materials containing identifiers and keys will be completed.

We will receive the coded participant data from MRI scan at BIDMC. The MRI data will allow for participant MRI to be imported into the Stimweaver software.

Foreseeable Risks, Potential Benefits, Compensation, and Cost to Participants

Potential medical risks of study procedures:

TESTS OF WALKING AND PHYSICAL FUNCTION: The proposed walking tests have been adapted from the large-scale, population-based MOBILIZE Boston study (PI: [name]) and multiple completed and ongoing clinical studies within the Clinical Research Laboratory at IFAR. They have been designed to be safe for individuals of varying risk and conditioning levels including older adult fallers. The physical activity associated with these tests is of low to moderate intensity. Potential risks include strains, sprains, muscle soreness, and light-headedness. In rare instances, more serious side effects such as an injurious fall may occur. For all functional tests, a trained "spotter" will stand behind or close to the subject to provide stabilizing assistance if necessary. Subjects will be instructed to stop performing or skip any test that makes them feel uncomfortable. Adequate rest will be given in between each test, and any reusable equipment will be cleaned with disinfectant after each use.

MAGNETIC RESONANCE IMAGING (MRI): Participants will have the option to participate in one brain MRI. They will rest in a horizontal position on the imaging table that slides into a magnetic field. All studies performed under this protocol will not exceed the FDA guidelines for magnetic resonance in any way. Therefore, the risks assumed by the participant are the same as in any noninvasive protocol involving whole body MRI. The presence of metal objects could cause a burn injury, but by following strict MRI exclusion guidelines, this risk will be minimized. Participants may feel claustrophobic or anxious during the procedure and they may experience musculoskeletal or back discomfort lying on the scanner table. The MRI makes loud banging noises as it takes images. Under some circumstances nerve stimulation may occur, which may be experienced as a mild twitching reaction in limbs and/or lower back muscles. Such effects are rare and scan settings are kept well below the levels where such effects are known to occur. MR imaging also requires the use of radio waves that can cause a mild warming similar to exposure to hot weather. Body temperature may increase but by less than two degrees Fahrenheit. Participants will be instructed to inform MRI personnel should they experience discomfort due to warming and the procedure will be stopped.

We may need to contact a participant's health care provider to ask him/her for documentation related to whether it is safe for the participant to have an MRI of their brain. For example, if they have had cataract surgery, we would need to verify the name, make, and model of the lens that was implanted. This is for safety purposes. If we need to contact a participant's health care provider, we will ask the participant for their written permission to do so.

TRANSCRANIAL DIRECT CURRENT STIMULATION (tDCS): tDCS has been widely used during the last decade demonstrating non-significant risk to participants. Expected side effects include:

1) Sensations reported by subjects under the electrodes: (These sensations can sometimes continue throughout and for a brief period following completion of the tDCS but usually resolve shortly after the initiation of tDCS)

- Mild tingling (20-70%)
- Light itching (30-40%)
- Slight burning (10-22%)
- Discomfort or mild pain (10-18%)

2) Other effects that can occur both during and after tDCS include:

- Mild fatigue (15%)
- Skin redness (20%)
- Headache (10-15%)
- Difficulties in concentration (11%)

3) Additionally the following rare side effects have been described:

- Nausea (<1%)
- Nervousness (<1%)
- Although it has never been reported in tDCS, seizures are a theoretical risk. Individuals with a history of seizures and/or a diagnosis of epilepsy will therefore be excluded from this study.

Potential psychosocial (non-medical) risks of study procedures:

TESTS OF MENTAL FUNCTION: Risks associated with answering these cognitive test questions are minimal, but participants may experience mental fatigue and/or anxiety during this form of testing.

INCONVENIENCES: We will minimize the risk to subjects in this study by excluding those with conditions listed in the exclusion criteria. The proposed protocol requires multiple visits and therefore considerable participant burden with respect to time and effort. Our study team has a strong track record of successful clinical research requiring similar participation, and retention has been high in these projects.^{118,205} The Clinical Research Laboratory at IFAR is located next to a cafeteria and equipped with comfortable seating, a TV, movies, books and magazines to keep individuals occupied during resting periods. Several additional strategies will be employed to minimize participant burden and maximize adherence to the protocol. We will:

- Develop a personal relationship between participants and members of the staff by matching research assistants with individual participants.
- Schedule appointments at convenient times with familiar staff.
- Explain to participants all aspects of their participation and follow up. We will demonstrate and practice study procedures before beginning data collection.
- Provide reminders of all appointments and follow-up phone calls. Include personal notes in the participant's data file to remember events in the life of the participant; these can be commented on at the next visit (e.g., birthday, birth of a grandchild).
- Provide snacks during all visits.
- Provide transportation for all visits, if required
- Provide valet or dedicated, on-site parking spaces.
- Compensate participants for visits.

Potential benefits to individual participants as a result of participating in the study:

Participants may not receive any significant health benefit from participation, although some may benefit from knowledge of their health status, as well as potential therapeutic effects of tDCS.

Participants will be provided up to a \$300 stipend to help cover the costs of their time spent completing study procedures. Specifically, they will receive the following amounts for each visit completed:

Visit 1A - In-person screening \$25

Visit 1B- Baseline assessment \$25

Visit 2 – Optional MRI visit - \$50

Visits 3- 6: Brain stimulation and Dual tasking assessment visits – one visit per week over 4 weeks; \$50 for each visit = total of \$200

Participants will receive a check in the mail within eight weeks of study participation.

Potential benefits to study population, community or society:

We believe that the potential benefits of understand and optimizing tDCS as a noninvasive intervention to improve dual task standing and walking in older adults outweigh the above-outlined potential risks to participants, which are expected to be minor, transient and relatively rare.

Provisions for medical care and available compensation in the event of injury:

Any subject who suffers an adverse event during the conduct of study protocols at Hebrew SeniorLife will be given immediate medical care at the Hebrew SeniorLife by the medical investigators, and, if the event meets the definition of a serious adverse event, the participant will be removed from the study, and will be referred to their primary care physician for ongoing care. The treating provider will bill the insurance company or other third parties, if appropriate, for the care a participant receives for any injury. We will try to have these costs paid for, but the participant may be responsible for some of them. For example, they may be responsible for payment of any deductibles and co-payments required by the insurer. There are no plans to provide any compensation for an injury beyond what is described above, should one occur.

If the event does not meet the criteria of a serious adverse event, and the participant is willing and able to continue, he/she will be able to continue and complete the study.

Definitions of Adverse Events and Serious Adverse events for the study

An adverse event is any untoward medical occurrence in a participant, whether or not is causally related to the study. An adverse event can therefore be any unfavorable and unintended sign (including an abnormal laboratory finding, for example), symptom or disease temporally associated with the study. Adverse events will be recorded on the appropriate case report forms and source documents. The investigator and/or trained staff member will evaluate all adverse events as to their severity and relation to the test article. The severity of adverse events will be graded as follows:

- Mild: Awareness of a sign or symptom but easily tolerated.
- Moderate: Discomfort sufficient to cause interference with usual activity or to affect clinical status.
- Severe: Incapacitating with inability to do usual activity or to significantly affect clinical status.
- Life Threatening: The participant was at immediate risk of death from the adverse event as it occurred.

The Investigator will also assess the relationship of any adverse event to study, based upon available information, using the following guidelines:

- 0 = Unlikely: No temporal association, or the cause of the event has been identified.
- 1 = Possible: Temporal association, but other etiologies are likely to be the cause; however, involvement of the study procedures cannot be excluded.
- 2 = Probable: Temporal association, other etiologies are possible, but not likely.

A serious adverse event is any experience that results in any of the following outcomes: death, is life threatening, inpatient hospitalization or prolongation of hospitalization, a persistent or significant disability/incapacity. Important medical events that may not result in death, be life-threatening, or require hospitalization may be considered a serious adverse event when, based upon appropriate medical judgment, they may jeopardize the patient or participant and may require medical or surgical intervention to prevent one of the outcomes listed in this definition.

Unanticipated problems and adverse events will be reported according to the Hebrew SeniorLife's IRB written guidelines for interventional studies. Serious adverse events will be reported to the Hebrew SeniorLife's IRB within 24hrs by fax or email, with a written report submitted within 5 business days of learning of the event, and submission of the incident via the eIRB system within one week of learning of the event. This form will record any adverse symptoms and/or study protocol deviations.

All adverse events/study incidents will be reported to the HSL IRB, according to policy, within 5 business days of learning of the event, and to submit the incident via the eIRB system within one week of learning of the event.

Data Safety Monitoring Board

Only those listed on the approved IRB protocol will have access to subject data. Subject data will be coded and locked in a file cabinet in a locked office. Identifying information will not be used during discussion, presentation or research publication. The criteria for discontinuing a participant's participation include the participant's request, as well as any unexpected life-threatening or potentially disabling event, including syncope, an injurious non-accidental fall, hemodynamic collapse, stroke, transient ischemic attack, dysrhythmia, renal insufficiency, angina, myocardial infarction, anaphylaxis, acute hemorrhage, or hospitalization for acute illness. Any adverse events that take place during testing will be reported by the PI ([name]) to [name], Director of Institute for Aging Research, Professor of Medicine at HMS and Chief of Gerontology at BIDMC and recorded in the database. Drs. [name] and [name] will have primary responsibility for monitoring participant safety in the trial. The investigators will be responsible for reviewing each adverse event in a timely fashion, and reporting all incidents to the DSMB in accordance with the established DSMB charter, and preparing a summary report. Any adverse events will be reported to the Hebrew SeniorLife IRB according to written guidelines.

Dissemination of Results

Results will be disseminated through publications in peer-reviewed medical journals, presentations at national meetings, and announcements on the HSL website and other public media.

To comply with the dissemination of NIH-funded clinical trial information, we will register this clinical trial at ClinicalTrials.gov. We will ensure that results information is submitted to ClinicalTrials.gov as outlined in the policy, and according to the specific timelines stated in the policy. We also will ensure that informed consent documents for this clinical trial will include a specific statement relating to posting of clinical trial information at ClinicalTrials.gov. Hebrew SeniorLife's Institute for Aging Research has an internal policy in place to ensure that clinical trials registration and results reporting occur in compliance with policy requirements.
